2.5 Safety analysis

All safety data will be summarized descriptively based on the safety population. All of the safety analyses will be done using OC. If deemed necessary, any analyses may be repeated using OC, BOCF, or MI as appropriate.

2.5.1 Extent of exposure

There will only be limited exposure to QM1114-DP since it is injected only once according to treatment group assignment. The number of subjects receiving a single dose of QM1114-DP and placebo, respectively, will be presented.

2.5.2 Adverse events

All AE data will be summarized by treatment group. Missing dates will be imputed as described below. AEs will be summarized by SOC and PT. AEs occurring before treatment will be presented in listings only. The MedDRA version used for the coding will be noted as a footnote in the tables and listings.

Print date:

2021-04-15 15:20

A summary of all AEs will be provided, which will include:

- number (%) of subjects who did not have an AE
- number (%) of subjects with at least one TEAE and number of events
- number (%) of subjects with at least one TEAE related to study product or injection procedure
- number (%) of subjects with at least one TEAE not related to study product or injection procedure
- number (%) of subjects with at least one TEAE leading to discontinuation
- number (%) of subjects with at least one serious TEAE.

Summaries of TEAEs (including the total number of events, number and percentage of subjects) will be displayed by treatment group according to the following:

- All TEAEs by SOC and PT
- Treatment emergent SAE by SOC, PT, maximum intensity (mild, moderate, severe), and causality
- Related TEAEs by SOC and PT, and maximum intensity (mild, moderate, severe)
- Unrelated TEAEs by SOC and PT, and maximum intensity (mild, moderate, severe)
- TEAEs leading to discontinuation by SOC and PT, and maximum intensity (mild, moderate, severe)
- TEAEs by SOC, PT, and action taken (none, medical treatment, non-pharmacological treatment, subject withdrawn)

For the subject level analyses, the number and percentage of subjects who experienced at least one of the events listed above will be summarized overall and for each SOC and each PT. System organ class and PTs will be presented in descending frequency first (by QM1114-DP group), and then alphabetically if there are ties. Each subject will contribute at most one count per summarization category. In other words, if a subject has more than one TEAE with same PT, the subject will be counted only once for that PT. Similarly, if a subject has more than one TEAE for a SOC, the subject will be counted only once in that SOC and PT. For the event level analyses, the counts of each respective event will be presented. In general, percentages will be calculated using the number of subjects in the safety population for the denominator. For the subgroup analyses (described in Section 2.5.2.1), percentages will be calculated using the number of subjects in the safety population for each respective sub-category as the denominator.

For the "action taken" summary specifically, subjects will be only counted in 'None' category if no other action was taken. The onset/duration summaries will be presented at the event level (i.e. will include multiple AEs within the same SOC and PT). Number of days to onset and duration of event will be summarized by SOC and PT, using mean, SD, minimum, maximum, and median statistics. Time to onset will be calculated as the first day with the AE minus the Day 0. Duration will be calculated as the last day with the AE minus the first day with the AE plus one. The text below lists the imputation rules for partial/completely missing dates. Missing stop date will not be imputed and therefore no duration will be calculated in these cases. Instead, the number of AEs that were ongoing at the end of the study will be given.

Handling of Missing/Partial Dates

While every effort will be made to obtain full, complete information on every reported AE, the following imputation rules will be followed for any respective missing AE data:

Doc id 43QM1901 Statistical Analysis Plan US - QM1114-DP - LCL 🖧 GALDERMA MA-43263

For the purpose of calculating treatment emergence, onset time, and duration, the following date imputation rules will used. Dates will be presented as is in the listings.

Start Date

If start date is completely missing, it will be assumed that the AE started on the treatment date.

Print date:

2021-04-15 15:20

- If the start date is missing the day, the first of the month will be used (i.e. UNK-JAN-2019 becomes 01-JAN-2019), provided the imputed date is on or after the subject's treatment date; otherwise, the day of treatment will be used.
- If the start date is missing the month, the month of 'June' will be used (i.e. 01-UNK-2019 becomes 01-JUN-2019), provided the imputed date is on or after the subject's treatment date; otherwise, the subsequent month after treatment will be used.
- If the start date is missing the year, the year of treatment will be used (i.e. 01-JAN-UNK becomes 01-JAN-2019), provided the imputed date is on or after the subject's treatment date; otherwise, the subsequent year after treatment will be used

End Date

- If end date is completely missing, it will be assumed that the AE is still ongoing and will not be imputed.
- If the end date is missing the day, the last of the month will be used (i.e. UNK-JAN-2019 becomes 31-JAN-2019)
- If the end date is missing the month, the subsequent month after the start date will be used.
- If the end date is missing the year, the year of treatment will be used (i.e. 01-JAN-UNK becomes 01-JAN-2019), provided the imputed date is after the start date; otherwise, the subsequent year after start date will be used.

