7.2.6.2 Reporting Procedures

7.2.6.2.1 Procedures for Reporting Adverse Events

The collection of AEs is from the time that a subject signs the ICF to their final visit.

At each post-enrollment visit, the Investigator (or sub-Investigator) will question the subject about AEs using an open non-persuasive question to elicit reporting of AEs, for example "Have you noticed any change in your health since the last visit?" Directed questioning and examination will then be performed as appropriate.

ion: 4.0

Effective

Print date:

2020-06-11 13:03

Any AE occurring during the AE reporting period, whether it is related to the study product or not, will be recorded immediately in the source document, and described on the AE form of the eCRF along with the date of onset, severity, relationship to the study product, and outcome, without omitting any requested and known information. Additional information will be requested under certain circumstances.

At study end, AEs assessed as related to the treatment or study procedure will be monitored until they have resolved or reached a stable condition. Other AEs will be monitored until the last visit if they have not resolved or reached a stable condition.

The Investigator will maintain all pertinent medical records in the subject's study file. If necessary and approved by the subject or their legal health care representative, the Investigator may contact the subject's personal physician or other health care provider(s) to obtain further details.

For SAEs (see Section 7.2.6.2.2) and pregnancies (see Section 7.2.6.2.3), the Sponsor is to be informed immediately by e-mail. The event must be reported to the Safety e-mail within 24 hours of receipt of the information (contact details in Section 7.2.6.2.2).

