9.1.3.2 Safety Analysis

All treatment related TEAEs by maximum intensity, treatment unrelated TEAEs by maximum intensity, treatment emergent SAEs by causality and maximum intensity, and action taken of treatment related TEAEs will be summarized by SOC and PT including number of subjects with at least one event, percentages, and number of events. All related TEAEs will also be summarized by time to onset and duration. In addition, a short summary of these presentations will be provided. AEs occurring before treatment will only be provided in subject data listings.

Data for hematology, blood chemistry, antibodies, and vital signs will be summarized by descriptive statistics with the value at each visit as well as the change from baseline. Results of ECGs will be summarized descriptively. The results of the urine pregnancy tests will be listed.

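### Adverse event duration is summarised from events with a stop date only, so the reported durations lean short; the impact is minor and the remedy cheap

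*SAP*

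**What the plan says.** Protocol 9.1.3.2 calls for the summary: "All related TEAEs will also be summarized by time to onset and duration". SAP 2.5.2 gives the method.

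- **Formula.** "Duration will be calculated as the last day with the AE minus the first day with the AE plus one". This needs a stop date.
- **Statistics.** "Number of days to onset and duration of event will be summarized by SOC and PT, using mean, SD, minimum, maximum, and median statistics". The summary is at event level, and no censoring method is given.
- **No stop date.** "Missing stop date will not be imputed and therefore no duration will be calculated in these cases". The next sentence adds: "Instead, the number of AEs that were ongoing at the end of the study will be given". The date rules in the same section agree: "If end date is completely missing, it will be assumed that the AE is still ongoing and will not be imputed". A partly missing end date is imputed, so those events keep a duration.

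Protocol 7.2.6.2.1 sets the follow-up. Events related to treatment or procedure are followed beyond study end until resolution or stabilisation. For the rest: "Other AEs will be monitored until the last visit if they have not resolved or reached a stable condition".

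Neither document says whether a resolution date learned after a subject's exit enters the locked database. Neither says how an end date is recorded for an event that has stabilised without resolving.

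**The concern.** An event still ongoing at last contact has a right-censored duration: it is known to have lasted at least so long. Leaving such events out and averaging the rest is a complete-case analysis in which the chance of exclusion rises with the quantity being measured. The mean, median and maximum then lean short, and a separate count of ongoing events does not correct them.

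Duration is a planned descriptive safety result. SAP 2.5.2.2 applies the methods of 2.5.2 to suspected toxin spread and hypersensitivity events, so any duration summary of those events inherits the rule. The protocol also uses Kaplan-Meier methods for duration of response (Protocol 9.1.3). The plan therefore handles censoring for the length of benefit but not for the length of adverse events.

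**Working it through.** The documents give no figure for event duration, the proportion ongoing or the expected bias, so there is nothing to reproduce. Every duration below is an assumption; the calculations show direction and range only.

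**Inputs from the documents.** A month is 28 days (schedule of assessments), so Month 6 is Day 6 × 28 = 168. The rule for events without a stop date is in SAP 2.5.2.

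**Closed form.** Assume exponential durations with mean m, observation for T days after onset, and no stop date obtained later. The plus-one day in the SAP formula is ignored. Then:

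- fraction ongoing: q = exp(−T/m)
- mean among resolved events: m − T·q/(1 − q)

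With onset at Day 7, T = 168 − 7 = 161:

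- m = 60: q = exp(−161/60) = 0.068; resolved-only mean 48.2 days, about 20% low.
- m = 90: q = exp(−161/90) = 0.167; resolved-only mean 57.7 days, about 36% low.

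For an event in a subject who exits at Day 28, T = 28 − 7 = 21:

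- m = 60: q = 0.705; resolved-only mean 9.9 days.
- m = 90: q = 0.792; resolved-only mean 10.1 days.

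In the early-exit case the resolved-only mean hardly depends on the true mean.

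**Simulation over a wider range.** 400,000 events per scenario; exponential or log-normal (sigma 1) durations; onset uniform over Days 0–7 or Days 0–168; everyone followed to Day 168; no later stop dates. Cells give exponential / log-normal.

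| Assumed true median (days) | Onset (days) | Ongoing (%) | Resolved-only median (days) |
|---|---|---|---|
| 5 | 0–7 | 0.0 / 0.0 | 5.0 / 5.0 |
| 5 | 0–168 | 4.3 / 4.9 | 4.8 / 4.8 |
| 14 | 0–7 | 0.0 / 0.7 | 14.0 / 13.9 |
| 14 | 0–168 | 12.0 / 13.5 | 12.3 / 12.4 |
| 30 | 0–7 | 2.2 / 4.4 | 29.1 / 28.4 |
| 30 | 0–168 | 25.3 / 26.8 | 21.9 / 23.1 |
| 90 | 0–7 | 28.2 / 27.4 | 57.8 / 63.4 |
| 90 | 0–168 | 56.0 / 57.8 | 36.5 / 46.3 |

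Three things follow.

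- The bias runs one way, short, wherever follow-up cuts events off. The mean suffers more than the median: with a true median of 30 days and onset over Days 0–168, the resolved-only mean is 29.9 / 30.6 days against a true 43.3 / 49.7.
- Omission of longer events is a tendency. With onset spread over follow-up, 15 to 24% of the omitted events were shorter than the true median; they had simply started late.
- A Kaplan-Meier median with ongoing events censored came within 0.4 day of the assumed median in every scenario.

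**The case against.** The plan is open about the rule: ongoing events are counted and reported, and dates are listed as collected. No duration can be computed for an event without an end, and the analysis is descriptive. The protocol asks for the duration summary for related events, which are the ones followed past study end, and nothing in SAP 2.5.2 excludes a stop date obtained then. The figures that assume no date after Day 168 or after exit are therefore unfavourable cases. All of this stands, and it limits the weight of the point. It does not remove it: a count leaves the mean and median as they are, follow-up may end at stabilisation, and use of post-exit dates is not stated.

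Some stronger readings are tempting, and the documents do not support them.

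- A reader might infer that the longest events are all removed and only short ones remain. In fact an early event that resolves just before Month 6 keeps its full duration, and some omitted events are short and late.
- A reader might take the 4–6 months in Protocol 1.1 as the likely length of toxin-related events. That statement concerns the effect on facial lines. The examples of possible events in Protocol 1.3 are injection site reactions and headache, and no section gives event durations of 60 or 90 days.
- A reader might conclude that the comparison between arms is distorted. That needs arms that differ in early exits or event length, which the documents do not establish, and no test of event duration is planned.

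**Conclusion.** The point holds as a minor one. Applied as written, SAP 2.5.2 preferentially omits longer events from the duration statistics, so these lean short. The size depends on event length, timing of onset, early exit and whether post-exit stop dates are used, none of which the documents settle. The worked range runs from practically nothing for short events soon after injection to a substantial understatement for long, late or cut-off events, and its upper end rests on assumed durations and on no stop date arriving after follow-up ends. Efficacy results and the type I error rate are untouched.

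**What to change.** In SAP 2.5.2:

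1. Label the duration statistics 'resolved events only', and show the number ongoing beside them by SOC, PT and arm.
2. State that stop dates obtained in the post-exit follow-up of related events (Protocol 7.2.6.2.1) are used where available.
3. For related treatment-emergent events, add a Kaplan-Meier median duration by arm, overall and for PTs with enough events. Censor events lacking a stop date at the last date they were known to be ongoing.

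The cost is SAP wording and one extra descriptive table, and reported durations may become somewhat longer. Medians may be inestimable for sparse PTs, particularly with 75 placebo subjects planned. Several events can come from one subject and are not independent, so the estimates should be presented as descriptive only. It should also be confirmed that dates of post-exit contacts are captured, since the adverse event reporting period ends with the subject's participation (Protocol 7.2.6.1.5).

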7.2.6.1.2 Treatment Emergent Adverse Event (TEAE)

A TEAE is an event that emerges during or after treatment, having been absent pre-treatment, or worsens relative to the pretreatment state.

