1.5.1 Adverse events

Adverse events (AEs) are to be monitored throughout the course of the study. All AEs reported will be coded using the Medical Dictionary for Regulatory Activities (MedDRA, version in force at the time of database freeze) and classified by MedDRA preferred term (PT) and system organ class (SOC). AEs will be defined as treatment-emergent adverse events (TEAEs) if the AE had an onset time greater than or equal to the time of study treatment. The study period for the purpose of AE collection is defined as the period from the signing of a study specific informed consent to study exit

A two-point scale ("Yes" or "No" response) will be used for the causality assessments. The Treating Investigator should be asked to indicate a response to each of the following questions in the electronic Case Report Form (eCRF:):

- "Do you consider that there is a reasonable possibility that the event may have been caused by the study product?"
- "Do you consider that there is a reasonable possibility that the event may have been caused by the study product injection procedure?"

If either of these questions is answered with a 'Yes', the AE will be considered related.

AE endpoints include incidence and severity of TEAEs.

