will be used. In addition, the number and percentage of subjects reporting a concomitant medication/therapy will be summarized by reason (medical history, adverse event, concomitant procedure, contraception, or other). Therapies and procedures that started due to an AE will be summarized separately from those who did not start due to an AE.

ATC-3 and preferred name will be presented in descending frequency first based on the QM1114-DP group, and then alphabetically if there are ties. Each subject will contribute at most one count per summarization category. In other words, if a subject has more than one medication with same preferred name, the subject will be counted only once for that preferred name. Similarly, if a subject has more than one medication for an ATC-3 level, the subject will be counted only once in that ATC-3 level and preferred name. Concomitant procedures will also be presented and will follow the same methods specified for medical history.

Prior and concomitant medications/procedures will be presented by subject in a data listing.

Handling of Missing/Partial Dates

While every effort will be made to obtain full, complete information on every reported medication, the following imputation rules will be followed for any respective missing medication data:

For the purpose of determining whether a medication is considered prior or concomitant, the following date imputation rules will used. Dates will be presented as collected in the listings.

Start Date

- If the start date is completely missing, it will be assumed that the medication started on the study treatment date.
- If the start date is missing the day, the first of the month will be used (i.e. UNK-JAN-2019 becomes 01-JAN-2019), provided the imputed date is on or after the subject's study treatment date; otherwise, the day of study treatment will be used.
- If the start date is missing the month, the month of 'June' will be used (i.e. 01-UNK-2019 becomes 01-JUN-2019), provided the imputed date is on or after the subject's study treatment date; otherwise, the subsequent month after study treatment will be used.
- If the start date is missing the year, the year of study treatment will be used (i.e. 01-JAN-UNK becomes 01-JAN-2019), provided the imputed date is on or after the subject's study treatment date; otherwise, the subsequent year after treatment will be used.

End Date

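### The partial-date rules in SAP 2.5.2 can turn AEs known to predate treatment into TEAEs, and SAP 1.5.1 omits the protocol's worsening criterion

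*SAP*

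**What the plan says.** SAP 2.5.2 states what its AE date rules are for: "For the purpose of calculating treatment emergence, onset time, and duration, the following date imputation rules will used". For a partial start date they work as follows.

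- Day missing: use the first of the recorded month if that is on or after treatment; "otherwise, the day of treatment will be used".
- Month missing: use June if that is on or after treatment; "otherwise, the subsequent month after treatment will be used".
- Year missing: use the treatment year if that is on or after treatment; "otherwise, the subsequent year after treatment will be used".

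No rule distinguishes a recorded month or year that is earlier than treatment from one that leaves the order open. No rule compares the imputed start with a recorded stop. SAP 2.3.4 applies the same start-date logic to medications (day missing: "otherwise, the day of study treatment will be used"; month missing: "otherwise, the subsequent month after study treatment will be used").

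On the definition itself, SAP 1.5.1 classes an AE as a TEAE "if the AE had an onset time greater than or equal to the time of study treatment". Protocol 7.2.6.1.2 also includes an event that was present before treatment "or worsens relative to the pretreatment state". SAP 2.8 sets out to list every departure from the protocol's analyses; its one entry concerns the per-protocol sensitivity analysis. SAP 2.5.2 puts AEs that occur before treatment in listings only.

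**The concern.** Assigning the treatment date when the order of onset and injection is unknown is ordinary conservative practice. Here the same step is taken when the order is known. An AE whose recorded month ended before injection is tabulated as treatment-emergent, with an onset day that contradicts the record. Without a stop-date check, an event that resolved before injection can be counted as starting after it ended.

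The narrower TEAE definition works in the opposite direction. An AE that begins between consent and injection and then intensifies is a TEAE under the protocol but goes only to listings under the SAP.

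Incidence and severity of TEAEs is the first safety endpoint in protocol 2.1.4, and both documents plan summaries of AE onset and duration. Those are the outputs at stake.

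**Working it through.** The plan gives no figure to reproduce, so the check applies the rules literally.

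**Inputs.** Start-date rules and duration formula (last day minus first day plus one): SAP 2.5.2. AE collection from consent to final visit: protocol 7.2.6.2.1. At most 14 days from screening to baseline: protocol 8.1.1. Month = 28 days, so Month 6 is Day 168 ±5: protocol Table 2. Group sizes 225 and 75: protocol 9.2.3. Assumptions: treatment on 05-OCT-2020; a start imputed to the treatment day counts as treatment-emergent; a recorded day is kept when the month or year is imputed.

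**Step 1: the rules on partial AE starts.**

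| Recorded start | First imputation | After the rule | Study day | Order relative to treatment |
|---|---|---|---|---|
| UNK-SEP-2020 | 01-SEP-2020, before treatment | 05-OCT-2020 | 0 | Known: before |
| UNK-OCT-2020 | 01-OCT-2020, before treatment | 05-OCT-2020 | 0 | Open |
| 10-UNK-2019 | 10-JUN-2019, before treatment | 10-NOV-2020 | 36 | Known: before |
| 28-UNK-2020 | 28-JUN-2020, before treatment | 28-NOV-2020 | 54 | Open |
| 28-SEP-UNK | 28-SEP-2020, before treatment | 28-SEP-2021 | 358 | Before, given the collection period |

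The 2019 row shows only how the rule works: with a 14-day window, a known earlier year needs a screening period that crosses New Year. The last row is placed 185 days after the latest Month 6 visit (358 - 173), outside the period in which AEs are collected.

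**Step 2: stop date.** Take UNK-SEP-2020 with a recorded stop of 02-OCT-2020. The start becomes 05-OCT-2020, and duration = (2 - 5) + 1 = -2 days.

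**Step 3: does any partial start remain pre-treatment?** Every onset 1 to 14 days before treatment was run for 365 consecutive treatment dates, with day, month or year missing in turn: 365 × 14 × 3 = 15,330 records. None stayed pre-treatment.

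**Step 4: how many of these are certainly wrong?** Assume onsets spread evenly over the 14 days and treatment dates evenly over a year. A treatment on day d of a month (d = 1 to 14) has 15 - d onset days in the previous month, and the sum over d is 105.

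- Known month earlier than the treatment month: 12 × 105 / (365 × 14) = 1,260 / 5,110 = 24.7% of pre-treatment AEs with the day missing.
- Known year earlier than the treatment year: 105 / 5,110 = 2.1% of pre-treatment AEs with the month missing.

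**Step 5: effect on a table.** One wrongly counted subject with no other TEAE adds 1/75 = 1.3 points on placebo or 1/225 = 0.4 points on active.

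**Step 6: the definitions.** The protocol has two routes to a TEAE, new onset or worsening; SAP 1.5.1 keeps only the first. The date rules can therefore only add TEAEs, and the shortened definition can only remove them.

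**Step 7: medications.** UNK-MAR-2015 becomes 05-OCT-2020. If the drug stopped before treatment, the imputed start is later than the stop. The drug can then meet the SAP 2.3.4 definition of prior, which rests on the stop date, and also look new since injection.

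**The case against.** The strongest reply is about size. Pre-treatment AEs are collected for at most 14 days, and for none when screening and baseline fall on the same day. Only records whose known parts place onset before treatment are certainly wrong. The rules are identical in both arms of a blinded, randomised trial, and safety is summarised descriptively. All of that stands.

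A reader might infer several stronger things that the documents do not support.

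- **That worsening events are generally lost.** Protocol 7.2.6.1.1 makes clinically significant worsening of an existing condition an AE in its own right, and protocol 7.2.1 to 7.2.4 have post-injection abnormalities or clinically significant changes recorded as AEs. Most worsened medical history would therefore carry a post-treatment onset. The remaining gap is mainly AEs that start between consent and injection and then intensify, since neither document says that a new record is opened.
- **That prior medications broadly become concomitant.** Prior status depends on the stop date, ongoing drugs are concomitant whatever start is imputed, and listings show dates as collected.
- **That per-protocol membership changes.** SAP 2.3.2 bases exclusion on a review of deviations before unblinding, and nothing links it to imputed dates.

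It is also fair to say that any imputation for a known day and year with an unknown month is arbitrary, and that protocol 9.1.3.2 itself sends AEs occurring before treatment to listings. Neither point justifies overriding a recorded month, or leaving the two TEAE definitions unreconciled.

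**Conclusion.** The point holds as a defect of the safety tables. Followed as written, SAP 2.5.2 gives wrong treatment emergence and onset for any partial-dated AE whose record already places it before treatment, and it allows negative durations. SAP 1.5.1 departs from protocol 7.2.6.1.2 without saying so.

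The size is probably small. The documents give no count of partial dates, so treatment emergence can be misclassified in a few records; no rate can be stated. The shares of about 25% and 2% rest on evenly spread onsets and treatment dates and apply only to pre-treatment AEs with the relevant part missing. The primary efficacy analysis is untouched, and no bias between arms is shown.

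**What to change.** In SAP 2.5.2:

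- Keep an AE pre-treatment when its known month or year, or its known stop date, precedes treatment.
- Use the treatment date only when the known parts, read with the consent and final-visit dates, leave the order open.
- Never impute a start later than a recorded stop.

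In SAP 2.3.4, add the same check that a medication's imputed start is not after its stop.

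In SAP 1.5.1, restore the protocol's worsening criterion, and say how an AE that begins before injection and then intensifies is recorded. If the narrower definition is intended, list it in SAP 2.8 with a reason.

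Under the revised rules, UNK-SEP-2020 stays before a 05-OCT-2020 treatment, while UNK-OCT-2020 still goes to the treatment day. The cost is a few lines of text and a small change to the date program, with no effect on endpoints, sample size or conduct. If the SAP is already final, SAP 2.1 provides for reporting the change in the study report.

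### Two partial stop-date rules in SAP 2.5.2 give wrong adverse event durations: a one-day event with the stop year missing becomes 366 days, and a missing stop month always moves resolution past the onset month

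*SAP*

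**What the plan says.** SAP 2.5.2 states the scope of its date rules: "For the purpose of calculating treatment emergence, onset time, and duration, the following date imputation rules will used". The duration formula is: "Duration will be calculated as the last day with the AE minus the first day with the AE plus one". Duration is then summarised at event level by system organ class and preferred term, with mean, SD, minimum, maximum and median. Protocol 9.1.3.2 asks for the duration of all related treatment-emergent AEs.

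For partial stop dates, the End Date list in SAP 2.5.2 has three rules:

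- Day missing: "If the end date is missing the day, the last of the month will be used".
- Month missing: "If the end date is missing the month, the subsequent month after the start date will be used".
- Year missing: the treatment year, "provided the imputed date is after the start date; otherwise, the subsequent year after start date will be used".

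A wholly missing stop date is outside this point: "Missing stop date will not be imputed and therefore no duration will be calculated in these cases". The start-date rules in the same section accept an imputed date that falls on or after treatment. The stop-year rule accepts only a date later than the start. SAP 2.3.4 has matching month and year rules for medication stop dates.

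**The concern.** The duration formula adds one day so that an AE starting and stopping on the same date counts as one day. The stop-year rule does not admit such an AE: a stop on the start date fails its test and is sent to the following year. The fallback, read literally, also skips the onset year when the AE began in the calendar year after treatment.

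The month rule never considers the onset month, although short AEs usually end in the month they began. It has no check against onset or against a recorded stop year.

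With 225 active and 75 placebo subjects planned, many preferred terms may hold few events. One record moved by a year would then set the maximum and dominate the mean of its row. SAP 2.5.2.2 applies the same methods to suspected toxin-spread and hypersensitivity events, where rows may be smaller still.

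**Working it through.** **Inputs.** Duration D = stop − start + 1 (SAP 2.5.2). The month and year rules are as quoted. A study month is 28 days (Protocol Table 2, SAP Appendix F), so Month 6 is 6 × 28 = Day 168. The documents give no enrolment dates, so the calendar dates below are assumed examples.

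**The plan's own examples.** The rules reproduce both: UNK-JAN-2019 becomes 31-JAN-2019, and 01-JAN-UNK becomes 01-JAN-2019. The second gives no start date. It works only if onset was before 1 January 2019, which with treatment in 2019 means before treatment.

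**A. One-day AE, stop year missing.** Treated and onset 02-NOV-2020, stop recorded as 02-NOV-UNK. The treatment year gives 02-NOV-2020, which is not later than the start, so the stop becomes 02-NOV-2021. D = 365 + 1 = 366; the true value is 1. Taking the fallback to mean the next such date after onset gives the same result.

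**B. Onset in the calendar year after treatment, stop year missing.** Treated 02-NOV-2020 (Day 168 is 19-APR-2021), AE 10-JAN-2021 to 14-JAN-UNK. The treatment year gives 14-JAN-2020, before onset. Read literally, the fallback gives 14-JAN-2022: D = 369 + 1 = 370. Read as the next such date after onset, it gives 14-JAN-2021: D = 4 + 1 = 5, which is correct.

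**C. Stop month missing, resolved in the onset month.** Onset 10-NOV-2020, stop 12-UNK-2020, truly 12 November. The rule gives 12-DEC-2020: D = 32 + 1 = 33 instead of 3. No alternative reading avoids this.

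**D. December onset, stop month missing.** Onset 10-DEC-2020, stop 15-UNK-2020, truly 15 December. Keeping the recorded year gives 15-JAN-2020: D = −330 + 1 = −329. Carrying the year forward gives 15-JAN-2021: D = 36 + 1 = 37, which overrides the recorded year. The true value is 6.

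**How often.** The rules were applied to every 2020 treatment date, onset Day 0 to 168 and true duration 1 to 14 days, keeping AEs that ended by Day 168 and weighting all cases equally:

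| Rule and reading | Result |
|---|---|
| Month missing, recorded year kept | exact 21%; at least 28 days late 70%; negative 7%; non-existent date such as 31 September 2% |
| Month missing, year carried forward | exact 21%; at least 28 days late 77%; negative 0%; non-existent date 2% |
| Year missing, literal | at least 365 days late 28% |
| Year missing, next such date after onset | at least 365 days late 7%, all one-day AEs |

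These shares describe the rules over an artificial grid. They do not predict error rates in this trial.

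**Effect on one table row (assumed data).** Nineteen 5-day AEs and one 1-day AE have mean (19 × 5 + 1)/20 = 4.8 days and maximum 5. If the 1-day AE lacks its stop year, the mean is (95 + 366)/20 = 23.05 days and the maximum 366.

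**The case against.** **Materiality.** This argument largely stands. AEs are asked about at every visit, and the data pass logical checks and manual review (Protocol 10.3). Listings show dates as collected, and the median is reported. A record with a known day but an unknown month or year should be rare.

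**Reading of the rules.** A reader might infer that the plan must produce negative durations, or that every AE starting in the year after treatment gains a year. Cases B and D show that both depend on the literal wording, and a sensible programmer could read it otherwise. Both also need follow-up that crosses a calendar year; a subject treated by 16 July 2020 reaches Day 168 within 2020. Cases A and C need neither condition.

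**Late stop dates.** A reader might also infer that any stop after study exit, or any duration above 168 days, is an error, because SAP 1.5.1 ends AE collection when the subject leaves the study. The documents do not support that. Protocol 7.2.6.2.1 follows related AEs after study end until resolved or stable, and 7.2.6.2.2 follows serious AEs until satisfactorily resolved. A late stop can be real, and a cap at exit could truncate or discard valid data.

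**Choice of convention.** Any single imputation often misses the true date, and the SAP leans late for a missing day as well. That is fair as far as it goes, but it does not justify ruling out the onset month altogether or failing a one-day AE.

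**Conclusion.** Both rules are wrong as written. The stop-year test turns a one-day AE into 366 days, and the stop-month rule adds about 30 days to any AE that ended in its onset month, except where its literal reading gives an earlier or non-existent date. These results need no assumption beyond a partial stop date occurring. The 370-day and negative cases are conditional on the literal reading and on follow-up crossing a calendar year.

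The error is large per record and small in total. It reaches only descriptive AE-duration summaries. The number of partial stop dates is not given and is probably small. AE incidence and all efficacy results are unaffected. The correction is worth making because the alternative is either wrong safety figures or an undocumented programming decision.

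**What to change.** Replace the month-missing and year-missing stop-date bullets in SAP 2.5.2 with one rule:

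- Impute the first calendar date on or after the AE start date that agrees with every recorded part of the stop date. Never move a recorded month or year.
- If no such date exists on or before the later of study exit and the last documented AE follow-up, query the record and leave the duration missing.
- Do not cap imputed dates at study exit.

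Cases A to D then give 1, 5, 3 and 6 days.

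Make the same correction to the matching medication bullets in SAP 2.3.4. There the dates only separate prior from concomitant use. A medication may have begun years before the study, so check that the first compatible date is plausible.

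The cost is a few lines of SAP text and one changed date macro, with no new data and no protocol amendment. The downside is that, when the month is missing, the rule picks the shortest compatible duration: an AE that truly ran from 10 November to 12 December would be reported as 3 days instead of 33. A table footnote should state this and give the number of imputed stop dates.
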